7.1. Analysis Plan of Adverse Events (AEs)

7.1.1. Onset of AEs

Number and proportion of subjects with AEs among all the subjects enrolled in this study (i.e., subjects randomized to ARM-1, 2 or 3, and those who discontinued the study before Week 24) will be tabulated by System Organ Class (SOC) and Preferred Term (PT) (see the Protocol for the details of categories and summarization). Two or more AEs with the same MedDRA term may be reported in a single subject; in such case, the AEs will be interpreted and counted as 1 subject to the analysis. Furthermore, the number and proportion of subjects with AEs by highest severity will be tabulated by presence/absence of causality with the study treatment for each ARM.

Furthermore, the number and proportion of subjects with AEs will be tabulated for each treatment period (Week 0 to Week 24, and Week 24 to Week 48) by SOC and PT. Moreover, the number and proportion of subjects with AEs at Week 24 onward will be tabulated for each ARM (ARM-1, 2, and 3) by SOC and PT.

7.1.2. Incidences of AEs for which causality with the study treatment cannot be ruled out Treatment-emergent adverse events (TEAE) for which causality with the study treatment cannot be ruled out will be tabulated at each assessment timepoint for each ARM (ARM-1, 2, and 3) by SOC and PT. In addition, the number and proportion of subjects with AEs by highest severity will be tabulated for each ARM. The incidences of TEAEs for which

causality with the study treatment cannot be ruled out that occur from Week 24 to 48 will be compared between ARM-2 and ARM-3 using a Fisher's exact test.

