## 5.3 Withdrawal criteria

Subjects should be withdrawn from this study if applicable to any of the discontinuation criteria presented below. Upon withdrawal, subjects should undergo assessments and tests for early termination. Also, the reason for withdrawal should be as necessary explained to the subject, and treatment after withdrawal should be given in a faithful manner to ensure there will be no disadvantage to the subject.

Principal investigator/sub-investigator shall record the date of and reason for withdrawal in EDC. Also, for the traceable subjects, their clinical courses are followed up and reported to the Study Secretariat. Subjects withdrawn from this study do not need to be replaced regardless of the reason for withdrawal.

- 1) Subject wishes to discontinue his/her study treatment
- 2) Subject wishes to withdraw his/her consent
- 3) Serious (or significant) AE occurs, and the study treatment is determined to be difficult to continue
- 4) A comorbidity (complication, etc.) exacerbates, and the study treatment is determined to be difficult to continue
- 5) Definitive exacerbation of RA is confirmed
- 6) Use of bDMARDs other than ADA or use of JAK inhibitor
- 7) MTX at a dosage  $\geq 10$  mg/week cannot be maintained at Week 24 due to ADR, etc.
- 8) MTX at a specified dosage (ARM-2: 10 to 25 mg/week [the maximum dose should be set according to the package insert of each country], ARM-3: 6 to 8 mg/week) cannot be maintained after Week 24 due to ADR, etc.
- 9) An increased dosage of MTX is required after Week 24 due to loss of efficacy, etc.
- 10) Confirmed pregnancy
- 11) Confirmed critical protocol deviation
- 12) Found to be applicable to an exclusion criterion after enrollment in the study
- 13) Other reasons by which the study is not appropriate for continuation as judged by principal investigator/sub-investigator

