## 8 Adverse events

## 8.1 Definition

## 8.1.1 Definition of adverse event (AE)

AE is any untoward medical occurrence in a subject administered the study drug, whether or not it is related to the study treatment. That is, an adverse event is any exacerbation of conditions pre-existed prior to the start of study treatment, any untoward or unintended clinical signs, and abnormal change in vital signs.

Exacerbation of the underlying disease (RA) should also be handled as an AE if such exacerbation is beyond the scope of initial expectation. An abnormal change in clinical laboratory value or vital sign should be handled as an AE if it results in discontinuation of study treatment, requires intervention, or is otherwise determined to be an AE by principal investigator or sub-investigator.

AEs that occur or exacerbate after the initial dose and no later than Week 48 of study treatment shall be handled as an AE.

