## 8.2 **Procedures for collection, documentation, and reporting of SAEs**

Upon detection of an SAE, the principal investigator shall report all SAEs regardless of the causality with the study drug to the study secretariat (SAE Report Center) as promptly as possible (within 1 business day in principle) using the SAE report form (Attachment 1). The principal investigator shall also report the information to Hospital Director (also to the Ethical Review Board in South Korea and Taiwan) if he/she judges that the SAE is causally "related" to the study drug. When sub-investigators, etc. other than the principal investigator detect a suspected SAE, they shall report it to the principal investigator and Eisai Co., Ltd. within 2 business days after receiving the information. The Lead Principal Investigator reports a drug-related SAE to the Certified Review Board within the period specified by the Clinical Trials Act and also should report it to the principal investigators of the other study sites. In Japan, the principal investigators who receive the report shall report the event to Hospital Director of the study site to which they belong.

All SAEs that occur on or before the final study-related visit should be collected regardless of the causality with the study treatment. All SAEs must be followed up until they are resolved,

or their symptoms stabilize if not expected to be resolved. Any SAE after study completion, for which a causality with the study drug (or protocol-specified procedures) cannot be ruled out as judged by the principal investigator or sub-investigator, must be reported to the study secretariat regardless of the time from study completion.

It is important to complete the initial SAE report Form as detailed as possible including the evaluation of causality with the study treatment as determined by the principal investigator or sub-investigator.

Any follow-up information received on SAEs should be forwarded by the principal investigator to the study secretariat within 1 business day of its receipt. If the follow-up information changes the investigator's assessment of causality, this should also be noted on the follow-up SAE report form.

Preliminary SAE reports should be followed as soon as possible by detailed descriptions including copies of hospital case reports, autopsy reports, and other documents requested by the study secretariat.

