## 8.3 Follow-up of subjects after AEs

#### 8.3.1 Follow-up

All AEs must be followed up for 70 days from the final dose of study drug or until recovery, whichever comes first; provided that an SAE must be followed up until it is resolved, or its symptoms stabilize if not expected to be resolved.

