## 9.2.3.1 Adverse events (AEs)

AEs recorded in EDC will be reinterpreted with ICH Medical Dictionary for Regulatory Activities (MedDRA). AEs recorded in EDC will be reinterpreted to the closest MedDRA lowest level terms (LLT) (Ver. 19.0 or later version). Preferred term (PT) and system organ class (SOC) will also be entered in the database. Treatment-emergent adverse events (TEAE) means AEs not confirmed before the study treatment (MTX) and emerges for the first time after the start of study treatment. TEAE also includes:

- Events confirmed before the study treatment which disappears immediately before the start of study treatment, but reemerges during the study treatment; and
- Events confirmed before the study treatment, which becomes severer during the study treatment compared to the level of severity before the start of study treatment.

TEAE will be used for the analysis of AEs. The number (proportion) of subjects with TEAE in each ARM will be tabulated in SOC and PT. Two or more AEs with the same MedDRA term may be reported in a single subject; in such case, the AEs will be interpreted and counted as 1 subject pertinent to the analysis, and also the AE with the highest severity will be counted in for the analysis on the number (proportion) of subjects with the TEAE. Furthermore, the number (proportion) of subjects with TEAE will be tabulated by the presence/absence of causality.

In addition, TEAE for which causality with the study treatment cannot be ruled out (ADR) will be tabulated in terms of SOC and PT, and the AEs with the highest severity will be counted in for the analysis on the number (proportion) of subjects.

The incidence of TEAE that occur from Week 24 to 48 will be compared between ARM-2 and ARM-3 using a Fisher's exact test or other relevant method.

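### The Week 24–48 adverse-event comparison of ARM-2 and ARM-3 uses crude subject proportions with no allowance for time at risk, although withdrawal ends participation

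*SAP*

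**What the plan says.** **The comparison.** Protocol 9.2.3.1: "The incidence of TEAE that occur from Week 24 to 48 will be compared between ARM-2 and ARM-3", by Fisher's exact test or another relevant method. SAP 7.1.2 fixes Fisher's exact test but applies it only to TEAEs whose causality cannot be ruled out. The SAP 7.1.1 statement that "the number and proportion of subjects with AEs at Week 24 onward will be tabulated for each ARM" is a descriptive table, not the test. SAP 9.1 lists no revision from the protocol.

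**Leaving the study.** Protocol 5.3 withdraws subjects from the study, not only from treatment. Grounds include a wish to stop treatment, an MTX dose that cannot be held after Week 24 because of an ADR, a needed MTX increase, and definite RA exacerbation. Under 6.1 the dose floor differs by arm: 10 mg/week in ARM-2, 6 mg/week in ARM-3.

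**How long events are collected.** Five places bear on this:
- 7.5: the AE row of the schedule ends in the column for Week 48 or early termination.
- 8.1.1: "AEs that occur or exacerbate after the initial dose and no later than Week 48 of study treatment shall be handled as an AE". Early termination is not mentioned.
- 8.2: "All SAEs that occur on or before the final study-related visit should be collected regardless of the causality with the study treatment". After study completion, an SAE is reportable only if causality cannot be ruled out.
- 8.3.1: "All AEs must be followed up for 70 days from the final dose of study drug", or until recovery if sooner.
- 5.3: for traceable withdrawn subjects, "their clinical courses are followed up and reported to the Study Secretariat". No schedule, duration or AE content is given.

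**The concern.** A crude proportion compares arms fairly only if their subjects are watched for similar lengths of time. Here a subject who leaves event-free at Week 30 has been observed for 6 of the 24 weeks but stays in the denominator as a full subject without an event. If one arm has more such departures, its proportion falls for a reason unrelated to safety.

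Unequal loss is plausible by design: the arms have different MTX dose floors, and a need for more MTX ends participation. The contrast also matters, because protocol 3.3 gives fewer dose-dependent MTX reactions as the expected gain from the lower dose. SAP 4.2 tabulates discontinuations by arm and SAP 4.4 describes MTX dose by arm, but neither is linked to the AE comparison.

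**Working it through.** **Inputs from the documents.** Group size: 110 per arm (protocol 9.4.1), used only as a sample size. No AE rate is given, and no dropout rate overall or by arm. The enrolment arithmetic reproduces: 220 / (0.85 × 0.90) = 287.6, hence 288. The step to 300 for dropouts is 12/300 = 4% of those enrolled, not split by arm or period. There is therefore no planned figure for the safety comparison to check, and everything below rests on assumed rates.

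**Model.** Over Weeks 24–48 (one unit of time), assume a constant event hazard λ, a constant dropout hazard μ, and dropout unrelated to AEs. For true 24-week risk P and dropout probability d:
- λ = −ln(1 − P), μ = −ln(1 − d)
- crude proportion = λ/(λ + μ) × [1 − (1 − P)(1 − d)]

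**Worked case, P = 40%.** λ = 0.511.
- d = 5%: μ = 0.051; 0.511/0.562 × (1 − 0.60 × 0.95) = 0.909 × 0.43 = 39.1%.
- d = 20%: μ = 0.223; 0.511/0.734 × (1 − 0.60 × 0.80) = 0.696 × 0.52 = 36.2%.

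The true risks are equal, but the crude proportions differ by 2.9 points.

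| True risk, both arms | Crude, 5% dropout | Crude, 20% dropout | Spurious difference |
|---|---|---|---|
| 10% | 9.75% | 8.98% | 0.8 points |
| 20% | 19.51% | 18.00% | 1.5 points |
| 40% | 39.08% | 36.19% | 2.9 points |
| 60% | 58.71% | 54.68% | 4.0 points |

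Over the same risks, 5% against 10% dropout gives 0.25 to 1.3 points, and 5% against 30% gives 1.3 to 6.9 points.

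**Effect on the test.** At 110 per arm and 60% true risk in both arms, Fisher's test at two-sided 5% rejects 3.4% of the time when both arms have 5% dropout, 6.9% with 5% against 20%, and 14.2% with 5% against 30%. At 40% risk with 5% against 20% it rejects 5.3% of the time.

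**Direction.** Take true risks of 50% in ARM-2 and 40% in ARM-3. With dropout of 15% in ARM-2 and 5% in ARM-3, the crude difference is 46.6 − 39.1 = 7.5 points instead of 10. With the dropout rates swapped, it is 48.9 − 37.2 = 11.7 points. The sign of the error follows the attrition.

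**Whether a rate removes it.** Expected person-time to first event or dropout is [1 − (1 − P)(1 − d)]/(λ + μ). At P = 40% this is 0.43/0.562 = 0.765 and 0.52/0.734 = 0.708. The rates are 0.391/0.765 = 0.511 and 0.362/0.708 = 0.511, so the rate ratio is 1.0, as it should be under this model.

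**The case against.** **The direction is not established.** A reader might infer that the error favours ARM-3, because ARM-2 subjects who leave for an ADR are already counted while ARM-3 subjects who leave for lost efficacy are event-free. The documents do not support this. The efficacy withdrawal rules in 5.3 are not limited to one arm. Under 8.1.1, RA worsening beyond initial expectation is itself an AE, so such a departure may already count. An ARM-2 subject withdrawn for one reaction is also lost for later, different events, which lowers ARM-2 in individual SOC and PT rows. This objection stands in full.

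**Collection after withdrawal.** A reader might also infer that AE recording definitely stops at early termination, or that later information never reaches EDC. Neither is stated. The first is inferred from the schedule and the final-visit wording. Against the second, 7.4.1 requires all AEs in the study to be recorded in EDC, and 13.1 routes all data except SAE reports through it. What stands is narrower: no section clearly requires new non-serious AEs to be recorded after withdrawal.

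**The effect is small and conditional.** If every extra withdrawal follows an AE already counted, the any-AE proportion is not lowered. Equal attrition at equal risk gives no spurious difference, so a shortfall within one arm does not measure the problem. Events clustered soon after Week 24 would shrink the effect. At 110 per arm and 50% incidence, the 95% CI half-width is 1.96 × √(2 × 0.25/110) = 13 points, well above the 0.8 to 4 points illustrated. These points limit the size of the concern but do not remove it.

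**A rate has assumptions of its own.** First events per patient-year need withdrawal unrelated to AE risk and a roughly constant hazard. That is correct and is why the rate belongs beside the proportions, not in their place.

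**Conclusion.** The concern holds in a limited form. The planned Week 24–48 comparison treats all subjects in an arm as equally observed, while the protocol's rules allow unequal observation, and nothing planned would correct for it. The arm with more loss before a first event can look safer; which arm that would be cannot be told from the documents. With equal true risk of 10% to 60% and dropout of 5% against 20%, the distortion is about 0.8 to 4 points. Those rates, the constant hazards and dropout unrelated to AEs are all assumptions. This is a worthwhile, inexpensive improvement to a contrast close to the trial's stated purpose, not a flaw that invalidates the safety analysis.

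Two inconsistencies need resolving as well: the collection limits for withdrawn subjects, and all TEAEs in protocol 9.2.3.1 against related TEAEs only in SAP 7.1.2.

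**What to change.** **SAP 7.1.** Keep the proportions and Fisher's test. Beside them, for all TEAEs and for related TEAEs in Weeks 24–48, report person-time by arm and first events per patient-year, with the ARM-3/ARM-2 rate ratio and 95% CI. A time-to-first-event estimate would serve equally well. End person-time at the first event, the study withdrawal or early-termination date, or Week 48, whichever comes first. State that this assumes withdrawal unrelated to AE risk and, for the rates, a roughly constant hazard.

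**Reconcile the wording.** Make protocol 5.3, 7.5, 8.1.1, 8.2 and 8.3.1 agree on how long new AEs and SAEs are recorded in withdrawn subjects. Settle whether the test covers all TEAEs, related TEAEs or both, and record any departure from the protocol in SAP 9.1. No new follow-up period is proposed. Applying the 70 days of 8.3.1 to new events would add site work without equalising observation: after a last dose at Week 30 it covers 10 of the 18 weeks left to Week 48.

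**Cost.** One extra table and its stated assumptions, plus a wording clarification. Protocol 5.3 already puts the withdrawal date in EDC, and the planned period tables already need AE onset timing, so the rates need no new data.

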## 4.1.2 Secondary endpoints

- SDAI remission rate at Week 24
- SDAI remission rate at Week 48 in MTX Monotherapy Group

- ACR20, ACR50, and ACR70 response rate at each assessment timepoint
- HAQ remission rate at each assessment timepoint
- SDAI, CDAI, DAS28-ESR, and DAS28-CRP at each assessment timepoint, and change from baseline to each assessment timepoint
- Tender joint count, swollen joint count, VAS (physician- and patient-reported), HAQ, CRP, ESR, MMP-3, RF, and anti-CCP antibody at each assessment timepoint, and change from baseline to each assessment timepoint
- Modified total sharp score (mTSS) at each assessment timepoint, and change from baseline to each assessment timepoint
- Structural remission (mTSS  $\leq 0.5$ ) rate at each assessment timepoint
- Vital signs and laboratory findings at each assessment timepoint, and change from baseline to each assessment timepoint
- Status of AE (Up to Week 24, and up to Week 48 for each ARM)

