## 9.4.1 Sample size selection

Assuming that the SDAI remission rate is 30% for both ARM-2 and ARM-3, and the noninferiority margin is -15%, the number of subjects required for the lower bound of a twotailed 90% confidence interval for the intergroup difference in SDAI remission rate to exceed the non-inferiority margin at 80% power of detection would be 220 subjects in total (110 in each group).

Past reports suggest that the remission rate of MTX monotherapy is about 15%. Also, it has been reported that about 10% of patients cannot continuously receive MTX  $\geq$ 10 mg/week (Atsumi T, et al. 2016: 75-83). Thus, in order to randomize 220 subjects between ARM-2 and ARM-3, 288 subjects need to be enrolled, and considering some dropouts, a sample size of 300 subjects was selected as the target number of subjects to be enrolled.

<Justification for the estimated SDAI remission rate in ADA/MTX-Reduced Dose Group (ARM-3)>

The estimated SDAI remission rate in ARM-3 was calculated in reference to the results of the MTX Monotherapy  $\rightarrow$  ADA+MTX Group in HOPEFUL 1 Study in which Japanese MTX naïve patients receiving ADA+MTX or MTX alone for 26 weeks, and then, all subjects receiving ADA+MTX for another 26 weeks (Takeuchi T, et al. 2014: 536-43). Since the maximum dosage of MTX in HOPEFUL 1 Study was 8 mg/week (6.6±0.8 mg/week: Mean±SD), the results cannot be directly extrapolated to this study in which the maximum dosage of MTX up to Week 24 will be 16 mg/week; yet, the results would be appropriate to use as a reference for the SDAI remission rate in ARM-3 in which the dosage of MTX will be reduced to 6 to 8 mg/week from Week 24 onward. ARM-3 is designed for patients who have not achieved to SDAI remission at Week 24; thus, assuming that the subjects with SDAI remission at Week 26 in HOPEFUL 1 Study (20 subjects = 163 subjects × 12%) remain to be remission at Week 52, the Week-52 SDAI remission rate among the subjects with SDAI non-remission at Week 26 was calculated to be 31.5% [45/143 subjects, that is (65 subjects - 20 subjects)/(163 subjects -20 subjects)]. Therefore, the SDAI remission rate in ARM-3 was assumed to be 30%.

<Justification for the estimated SDAI remission rate of  $\leq$ 3.3 in ARM-2 (ADA/MTX-MTD Group)>

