3.1.3. Safety analysis set

The Safety Analysis Set is defined as a group of subjects who receive study drug (MTX) and have evaluable safety data at 1 or more time points following the administration of study drug (including subjects who discontinued the study before Week 24 as well as those randomized to ARM-1, 2 or 3).

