7.2. Analysis Plan of Clinical Laboratory Values and Vital Signs

For continuous variables, descriptive statistics of measurements at each assessment timepoint and their changes from baseline will be calculated for each ARM (ARM-1, 2, and 3). Furthermore, analysis of covariance (ANCOVA) adjusted by country will be performed to make a comparison between ARM-2 and ARM-3, and calculate the estimate of difference between the treatment arms and its two-tailed 95% confidence interval. In addition, descriptive statistics will be calculated, being stratified by country.

As an order categorical variable, clinical laboratory values will be categorized to Lower than the reference (L), Within the reference (N), and Higher than the reference (H), and then the number and proportion of subjects by L, N, and H will be presented in a shift table (baseline vs. each visit during treatment) for each ARM (ARM-1, 2, and 3). In addition, the maximum and minimum values after the start of treatment will be presented in a shift table for comparison with baseline. Furthermore, Wilcoxon rank sum test will be performed to make a comparison between ARM-2 and ARM-3.

Descriptive statistics of vital signs (diastolic blood pressure, systolic blood pressure, pulse rate, body temperature) and body weight at each assessment timepoint and their changes from baseline will be computed for each ARM (ARM-1, 2, and 3). Furthermore, analysis of covariance (ANCOVA) adjusted by country will be performed to make a comparison between ARM-2 and ARM-3, and calculate the estimate of difference between the treatment arms and its two-tailed 95% confidence interval.

8. Analysis Plan of Exploratory Endpoints

8.1. Erythrocyte MTX-PG Concentration at Weeks 0, 4, 8, 12, 24, 36, and 48 Descriptive statistics for erythrocyte MTX-PG concentrations as well as change from baseline and change rate from baseline will be calculated by country. In addition, descriptive statistics for Week 24 onward will be calculated at each assessment timepoint for each ARM (ARM-1, 2, and 3).

Pearson's product-moment correlation coefficient, Spearman's rank correlation coefficient, and their 95% confidence interval will be calculated at each assessment timepoint to evaluate the correlation of exposure to MTX, SDAI, mTSS, and ACR-N to erythrocyte MTX-PG concentration. Furthermore, cutoff values for AST increased, ALT increased, and WBC decreased, and their differences among the participating countries will be discussed.

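### Related adverse events and visit-by-visit laboratory shifts are tabulated only by ARM, leaving subjects withdrawn by Week 24 without an ARM no place in these tables

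*SAP*

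**What the plan says.** The Safety Analysis Set (SAP 3.1.3) is everyone who takes MTX and has some safety data afterwards, "including subjects who discontinued the study before Week 24 as well as those randomized to ARM-1, 2 or 3". SAP 3.2 assigns the analysis of safety variables to that set.

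The safety tables are then specified as follows.

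- SAP 7.1.2: related TEAEs "will be tabulated at each assessment timepoint for each ARM", with the arms listed as ARM-1, 2 and 3, by SOC and PT.
- SAP 7.1.1: subjects by highest severity, tabulated "by presence/absence of causality with the study treatment for each ARM". SAP 7.1.2 adds a further highest-severity table, again per ARM.
- SAP 7.2: laboratory categories in a "shift table (baseline vs. each visit during treatment) for each ARM (ARM-1, 2, and 3"), with the same three-arm list for the continuous laboratory and vital-sign summaries.

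The endpoint in Protocol 4.1.2 is "Status of AE (Up to Week 24, and up to Week 48 for each ARM"), which reads most naturally as no split by ARM for the first 24 weeks.

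Under Protocol 4.3.1 the IWRS issues ARM-1, 2 or 3 once the Week 24 assessments have been entered. Under Protocol 5.3 (criterion 7) and 6.1, a subject who cannot hold MTX at 10 mg/week or more at Week 24, because of an adverse drug reaction (ADR) or similar, is withdrawn. Protocol 9.4.1 plans on the basis that "about 10% of patients cannot continuously receive MTX" at that dose.

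**The concern.** Anyone withdrawn before ARM assignment is in the Safety Analysis Set but fits none of the columns ARM-1, 2 and 3. The loss is selective. For Weeks 0 to 24, those columns contain only subjects who reached Week 24 on at least 10 mg/week, so they are defined by an outcome of the treatment being summarised. The subjects left out include those withdrawn because of an MTX reaction.

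This matters because the objective (Protocol 3.2) includes relating MTX-polyglutamate concentration to the safety of MTX therapy, and the stated purpose (Protocol 3.3) is fewer MTX-related ADRs. If the related-TEAE table is read as the ADR profile of 24 weeks of MTX, it describes the subjects who tolerated the drug.

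**Working it through.** **1. Which outputs have a place for subjects without an ARM**

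| Output | Columns or population named | Subjects without an ARM |
|---|---|---|
| SAP 7.1.1, all-cause AEs by SOC and PT | All enrolled: ARM subjects and those who stopped before Week 24 | Included; withdrawal at Week 24 not clearly covered |
| SAP 7.1.1, all-cause AEs by period | Weeks 0-24 and 24-48, no ARM split | Included for Weeks 0-24 |
| SAP 7.1.1, highest severity by causality | Each ARM | No clear place |
| SAP 7.1.2, related TEAEs by SOC and PT | ARM-1, 2, 3 | None |
| SAP 7.1.2, highest severity | Each ARM | No clear place |
| SAP 7.1.2, Fisher test, Weeks 24-48 | ARM-2 against ARM-3 | Not applicable: randomised subjects only |
| SAP 7.2, by-ARM laboratory and vital-sign summaries | ARM-1, 2, 3 | None |
| SAP 7.2, descriptive statistics by country | Country | Not excluded |
| SAP 7.2, visit-by-visit laboratory shifts | ARM-1, 2, 3 | None |
| SAP 7.2, maximum/minimum laboratory shifts | No ARM named | Not excluded |

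SAP 4.2 (discontinuations) and 5 (demographics) also say per ARM, but each adds that subjects who stopped before Week 24 are included. SAP 7.1.2 and 7.2 carry no such addition.

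**2. How many subjects this concerns**

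Inputs from Protocol 9.4.1: 220 to be randomised, 15% in remission on MTX alone, 10% unable to continue at 10 mg/week or more.

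- Enrolment: 220 / ((1 - 0.15) x (1 - 0.10)) = 220 / 0.765 = 287.6, so 288. This reproduces the plan's figure, which is then raised to 300 for dropouts.
- MTX-intolerant: 0.10 x 288 = 28.8, or 0.10 x 300 = 30.
- Allowance for other dropouts: 300 - 288 = 12.

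On planning figures, then, about 29 to 30 intolerant subjects have no ARM, plus whichever of the other 12 leave before assignment. If all 12 did, the intolerant would be 28.8 / (28.8 + 12) = about 70% of the group.

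**3. How far a by-ARM rate can differ from the whole-set rate**

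Let r be the related-AE rate in subjects with an ARM, and q the rate in the 10% without one.

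- The ARM columns together show r.
- The Safety Analysis Set rate is 0.9r + 0.1q.
- Difference, whole set minus by-ARM: 0.9r + 0.1q - r = 0.1(q - r).

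The documents give neither q nor r, so both are assumed over a range. Difference in percentage points:

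| | r = 20% | r = 40% | r = 60% |
|---|---|---|---|
| q = 100% | 8 | 6 | 4 |
| q = 75% | 5.5 | 3.5 | 1.5 |
| q = 50% | 3 | 1 | -1 |

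A positive value means that the by-ARM tables understate the whole-set rate.

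**The case against.** The strongest reply is that the events are not lost. SAP 7.1.1 counts all-cause AEs in everyone enrolled and again for Weeks 0 to 24 without an ARM split, which meets the Protocol 4.1.2 endpoint. SAP 4.2 lists discontinuations before Week 24 with reasons. The maximum/minimum laboratory shift table and the by-country statistics name no ARM. Protocol 9.2.3.1 tabulates TEAEs by causality, and ADRs by SOC and PT, in sentences that name no ARM; SAP 7.1.1 defers to the Protocol for categories and summarisation, and SAP 9.1 records no departure from it. Since SAP 4.2 and 5 use the per-ARM phrase while including early discontinuations, the bare phrase need not exclude anyone.

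Most of this stands, and it limits the point. A reader might infer that these subjects' reactions vanish from the safety output; they do not. A reader might also infer that the comparison of the two MTX doses is compromised; the ARM-2 against ARM-3 comparison for Weeks 24 to 48 involves only randomised subjects.

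It does not remove the point. The all-cause tables carry no causality. Protocol 9.2.3 says that safety summaries are computed per ARM, so the silence in 9.2.3.1 is ambiguous. The related-TEAE table and the visit-by-visit shift table go beyond the bare phrase and list three arms. Followed as written, they leave subjects without an ARM no cell.

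**Conclusion.** The point holds as a reporting gap. The related-TEAE table, the visit-by-visit laboratory shift table and the by-ARM laboratory and vital-sign summaries have no place for subjects without an ARM; the severity tables have no clear place. This conflicts with SAP 3.1.3 and 3.2. The loss is causality attribution, severity by causality and visit-level shifts in about 30 of 300 subjects, if the planned 10% is right. No efficacy analysis and no randomised comparison is affected.

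A stronger reading, that the plan understates MTX toxicity by 6 to 8 points, is not supported. Those figures need every intolerant subject to have a related AE, together with a rate of 20% to 40% in the rest. The documents give no such rates, and withdrawal for intolerance may have reasons other than an ADR. Over the ranges assumed above the difference runs from -1 to +8 points. Understatement is the more likely direction because ADRs are the reason that the Protocol names for these withdrawals, but it is not guaranteed. A by-ARM column is also a valid description of its own arm; it misleads only if read as the rate for all treated subjects.

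**What to change.** - In SAP 7.1.1 (severity and causality), 7.1.2 and 7.2, report Weeks 0 to 24 on the full Safety Analysis Set, with a column for subjects never assigned an ARM and a total column. State that the new column includes withdrawals at Week 24 as well as before it, and align the SAP 7.1.1 description of all enrolled subjects with that.
- Keep the by-ARM columns for Week 24 onward.
- State in SAP 7.2 that the maximum/minimum shift table uses the full Safety Analysis Set, including early-termination values.

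The cost is SAP wording and two extra table columns. No new data are needed: AE severity, causality and laboratory results already go into EDC (Protocol 7.4, 8.1.3, 8.1.4), and Protocol 5.3 requires early-termination tests at withdrawal.
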